8.1. Multicenter Studies

Subjects will be screened and enrolled across five study sites for this study. Due to limited data from each site, no adjustment or stratification for site will be performed.

8.2. Other Strata and Covariates

In ANCOVA model, baseline MDS-UPDRS Part III total score will be set as covariates.

8.3. Examination of Subgroups

No subgroup analyses are planned for this study.

8.4. Multiple Comparisons and Multiplicity

Not applicable for this study.

8.5. Data handling conventions

8.5.1. Premature Withdrawal and Missing Data

For subjects who are withdrawn from the study prior to study completion, all data compiled up to the point of discontinuation will be used for analysis. All withdrawals will be included in all analyses up to the time of withdrawal.

There will be no imputation for missing data, unless otherwise stated.

8.5.2. Handling of Dropouts

No imputation of missing data will be performed for early termination subjects. All data collected prior to drop out will be listed and included in data summaries.

8.5.3. Additional/Unscheduled Assessments and Missing Data

Generally, missing dates/times will not be imputed. Adverse events with missing or partial dates will be handled such that in the absence of contradictory information an AE is treatment emergent. For a missing start date (where the stop date is after the date of first study drug administration) the start date will be imputed as the first study drug administration date. Similarly, for a missing stop date, the stop date will be imputed as the date of last visit. If a partial date is recorded, the following convention will be used to assign the AE:

- If a start date is missing the day information and the month/year is the same as the first study drug administration date, then use the first study drug administration date, else '01' will be used for the day. If a start date is missing the month and the year is the same as the first study drug administration date, then use the first study drug administration date, else 'January' will be used for the start month.
- If a stop date is missing the day information and month/year is the same as the last study date, then use the last study date, else the last day of the given month will be used for the stop day. If a stop date is missing the month and the year is the same as the last study date, then use the last study date, else 'December' will be used for the stop month.

Extra measurements (such as unscheduled or repeat assessments) will not generally be included in summary tables but will be included in subject listings. They may be used if a scheduled measurement is missing and the timing of the extra measurement is deemed suitable. They will be used in summary tables which are not 'time specific'; for example, summaries of maximum post dose values.

The original data will always be presented in the listings.

8.5.4. Assessment Windows

No visit windows will be applied to assessments. All assessments will be included in the listings.

8.6. Derived and Transformed Data

The required endpoints and variables will be derived by the Statistical Programmers at CNS using the derivations specified in Section 6.7 of this SAP.

8.7. Values of Clinical Concern

Not applicable for this study.

9. STUDY POPULATION

Subject disposition, demographics, baseline characteristics, prior and concomitant medication analyses will be conducted on the ITT Population. These results will be summarized by cohort and treatment group.

9.1. Disposition of Subjects

A disposition listing will present date of informed consent, date of randomization, study completion or withdrawal, the reason for withdrawal, if applicable and whether included in each analysis population, for each subject.

A listing of whether or not all inclusion and exclusion criteria were met and if not, which criteria were not met, by subject, will also be presented.

The following will be summarized, by cohort and randomized treatment group and for all subjects:

- The number of subjects randomized
- The number of subjects treated
- Number of subjects who completed the study
- Number of subjects withdrawn and reason for withdrawal
- Number of subjects in each analysis population

9.2. Protocol Deviations

Subject data will be examined for evidence of protocol deviations in order to assess how well the protocol was followed. These will be assessed for the final analysis.

All protocol deviations will be detailed in listings.

9.3. Demographic and Baseline Characteristics

Subject demographic and baseline variables (age, sex, childbearing potential, ethnicity, race, height, body weight and BMI at screening) will be summarized and listed, by cohort and treatment group.

The following baseline characteristics will be listed only:

- Medical history
- Smoking history
- Parkinson's Disease History
- Pregnancy test (Urine, Serum and FSH)

9.4. Treatment Compliance

The following drug administration data will be listed:

- Drug Administration: Benserazide
- Drug Administration: INP103/Placebo
- Administration of 'ON' Medication

9.4.1. Compliance to Study Drug

Not applicable for this study.

9.4.2. Measurement of Treatment Compliance

Not applicable for this study.

9.5. Prior and Concomitant Medications

The start dates of non-investigational medications will be used to assign medications into different categories.

- Prior medication: Any medication which started before the date of first study drug (benserazide, INP103 or placebo) administration. If the start date of the medication is not complete or missing, it will be treated as prior medication.
- Concomitant medication: Any medication which started on or after the date of first study drug (benserazide, INP103 or placebo) administration up to the final visit or premature study withdrawal, whichever is earliest.
- Prior and concomitant medication: Any medication which started before the date of first study drug (benserazide, INP103 or placebo) administration but continued after the date of first study drug administration.

Medications will be classified as a prior medication and/or a concomitant medication. If a medication has a missing or partial missing start/end date or time and it cannot be determined whether it was taken before the date of first study drug administration or concomitantly, it will be considered as both prior and concomitant.

Medications with a start date prior to the first administration of study drug and a treatment end data after the first administration of study drug will be assigned to both prior medication and concomitant medication categories.

Prior and concomitant medications will be coded by WHO-DDE Version MAR-2018. Concomitant medication data will be summarized by Anatomical Therapeutic Chemical (ATC) system (Level 4 for anti-PD medications and Level 2 for other medications) and drug preferred name. The summary table will show the number and percentage of subjects taking each medication by ATC Level and preferred name.

For the summaries of concomitant medications, subjects who take the same medication (in terms of the ATC Level and preferred name) more than once will only be counted once for that medication.

Prior medication and concomitant medications will be listed and concomitant medications will be summarized, separately, by cohort and treatment group and summary results will be presented in alphabetical order.

The following medications will be listed:

- Rescue OFF Tx Allowed
- Usual Morning anti-PD Medication
- Levodopa containing Medication

In addition, Rescue OFF Tx Allowed and Usual Morning anti-PD Medication will be summarized using frequency tabulations (Yes/No).

10. EFFICACY ANALYSES

The analyses of PDyn results will be treated as the exploratory analysis of preliminary efficacy in this study and all efficacy analyses will be conducted on the ITT population.

10.1. Change from baseline to 30 minutes post-dose in MDS-UPDRS Part III Score at Visit 3

For each subject, the individual scale from question 3.1 to 3.18 of MDS-UPDRS Part III questionnaire will be added as total score and it will be applied for following analysis of MDS-UPDRS Part III score.

The changes from baseline to 30 minutes post-dose in MDS-UPDRS Part III total score at Visit 3 will be summarized by treatment groups (INP103 35 mg, INP103 70 mg, INP103 140 mg, INP103 70 mg with 7.0 mg carbidopa, or placebo).

10.2. Change from baseline to post-dose timepoints in MDS-UPDRS Part III score

The changes from baseline in MDS-UPDRS Part III score will be summarized by time point (15, 30, 45, 60, 90 or 120 minutes for C1, C2 and C3; 30, 60, 90 or 120 minutes for C4) and treatment groups (INP103 35 mg, INP103 70 mg, INP103 140 mg, INP103 70mg with 7.0 mg carbidopa or placebo). In addition, the changes from baseline in MDS-UPDRS Part III score will be estimated using a Mixed Model for Repeated Measures (MMRM) with treatment group, time, and the interaction between treatment group and time point as fixed factors, and the baseline total score will be included as a covariate. The focus will be on the estimation of changes within each treatment group. An unstructured covariance structure will be used for the MMRM. In case the model does not converge with the unstructured covariance structure, the heterogeneous compound symmetry (CSH) or heterogeneous Toeplitz structure (TOEPH) will be used instead. The denominator degrees of freedom will be approximated using the Kenward-Roger method. The least squares (LS) means, standard errors and two-sided 95% confidence intervals will be provided for changes across time points within each treatment group.

In addition, the differences between each treatment group and placebo will be estimated across time points based on the same MMRM model, and LS mean, standard errors and 95% CI of differences will be presented.

Change from baseline in MDS-UPDRS III score will be plotted by each treatment group for each subject (y axis) against time from dosing (x-axis).

10.3. Cumulative proportion of responders by post-dose time point

The cumulative proportion of responders will be summarized by post-dose time point (15, 30, 45, 60, 90 or 120 minutes for C1, C2 and C3; 30, 60, 90 or 120 minutes for C4) and treatment groups (INP103 35 mg, INP103 70 mg, INP103 140 mg, INP103 70 mg with 7.0 mg carbidopa, or placebo) using frequency tabulations. Subjects that achieve response will count as a responder for all subsequent time points regardless of a return to “<30% improvement” post achievement of response.

10.4. Time to response

The time to response is defined as time from first dosing to the FIRST response of a 30% or greater improvement in MDS-UPDRS Part III total score post INP103/Placebo dosing of each patient. Subjects without response identified will be censored at the last assessment time. Survival analysis will be used to analyze the time to response. The analysis of time to response is based on the survivor function, which is the probability to survive or, more generally, to stay event-free beyond a certain point in time. The survival function will be estimated by the Kaplan-Meier method. The survival function will be summarized for 25th percentile, median, and 75th percentile and their 95% confidence intervals. The plot of Kaplan-Meier estimates for the treatment groups will be presented. The y-axis of Kaplan-Meier estimates will be plotted as cumulative event (response) rate (i.e. one minus survival rate).

10.5. Duration of response

Duration of response = *sum of all time intervals which observed a response.*

The duration of response will be calculated for each subject and summarized by treatment groups (INP103 35 mg, INP103 70 mg, INP103 140 mg, INP103 70 mg with 7.0 mg carbidopa, or placebo).

For example, if the subject achieves a response at 15, 45 and 90 and 120 minutes (data shown in table below), the duration of response will be calculated as the sum of the duration (95 minutes = 15 minutes + 0 minutes + 0 minutes + 15 minutes + 31 minutes + 34 minutes).

| Schedule Timepoint | Actual Time | Response* | Derivation for Duration of Response* | Duration of Response* |
|--------------------|-------------|-----------|--|-----------------------|
| Pre-dose | 10:00 | NA | NA | |
| 15 mins post dose | 10:15 | Yes | Actual time at "15 mins post-dose" minus the Actual time at "Pre-dose" | 15 |
| 30 mins post dose | 10:30 | No | NA | 0 |
| 45 mins post dose | 10:45 | Yes | Actual time at "45 mins post-dose" minus the Actual time at "30 mins post-dose" | 15 |
| 60 mins post dose | 11:00 | No | NA | 0 |
| 90 mins post dose | 11:31 | Yes | Actual time at "60 mins post-dose" minus the Actual time at "90 mins post-dose" | 31 |
| 120 mins post dose | 12:05 | Yes | Actual time at "90 mins post-dose" minus the Actual time at "120 mins post-dose" | 34 |

* Response is defined as an improvement of at least 30% in MDS-UPDRS Part III score from baseline

10.6. Area Under the Curve (AUC) of changes in MDS-UPDRS Part III scores from pre-dose to post-dose timepoints

AUC of changes in MDS-UPDRS Part III total scores from pre-dose to post-dose will be calculated by trapezoid formula by the following formula:

CONFIDENTIAL AND PROPRIETARY

Area under Curve of (*post-dose total score minus pre-dose total score in MDS-UPDRS Part III score*)

For each subject, AUC of changes in MDS-UPDRS Part III total scores from pre-dose to 15, 30, 45, 60, 90 and 120 minutes for C1, C2 and C3; 30, 60, 90 or 120 minutes for C4 will be calculated as: $AUC_{0-15\text{mins}}$, $AUC_{0-30\text{ mins}}$, $AUC_{0-45\text{ mins}}$, $AUC_{0-60\text{ mins}}$, $AUC_{0-90\text{ mins}}$ and $AUC_{0-120\text{ mins}}$. (omitting $AUC_{0-15\text{ mins}}$ and $AUC_{0-45\text{ mins}}$ for Cohort 4).

These AUC parameters will be summarized by each treatment groups (INP103 35 mg, INP103 70 mg, INP103 140 mg, INP103 70 mg with 7.0 mg carbidopa, or placebo).

Each AUC parameter ($AUC_{0-15\text{ mins}}$, $AUC_{0-30\text{ mins}}$, $AUC_{0-45\text{ mins}}$, $AUC_{0-60\text{ mins}}$, $AUC_{0-90\text{ mins}}$ and $AUC_{0-120\text{ mins}}$) will be analyzed with an Analysis of Covariance (ANCOVA) model with treatment group as a fixed factor and baseline MDS-UPDRS Part III score as a covariate. The least squares (LS) means, standard errors and two-sided 95% confidence intervals will be provided for changes within each treatment group. In addition, the differences between each treatment group and placebo will be estimated.

10.7. Individual Maximum response in MDS-UPDRS Part III scores from pre-dose to 15, 30, 45, 60, 90 and 120 minutes post-dose.

The individual maximum response scores will be defined as the maximum MDS-UPDRS Part III score post INP103/Placebo dosing from the baseline across all time points post dose (from 15, 30, 45, 60, 90 and 120 minute for C1, C2, C3 and 30, 45, 60, 90, and 120 minutes for C4) for each subject.

The individual maximum response scores will be summarized by each treatment groups INP103 35 mg, INP103 70 mg, INP103 140 mg, INP103 70 mg with 7.0 mg carbidopa, or placebo).

The individual maximum response scores will be analyzed with an ANCOVA model with treatment group as a fixed factor and baseline MDS-UPDRS Part III score as a covariate. The least squares (LS) means, standard errors and two-sided 95% confidence intervals will be provided for changes within each treatment group. In addition, the differences between each active treatment group and placebo and their 95% CIs will be estimated.

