12. STATISTICAL ANALYSES

This protocol section describes the statistical analyses as they are foreseen at the time of planning the study. A separate Statistical Analysis Plan (SAP) will be prepared prior to performing any unblinded analysis. The SAP will serve as a complement to the study protocol and supersedes it in case of differences.

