12.5. Pharmacodynamic Analysis

The changes from baseline in MDS-UPDRS Part III scores will be summarized by treatment groups and estimated using a Mixed Model for Repeated Measures (MMRM) with treatment group (INP103 35 mg, INP103 70 mg, INP103 140 mg, INP103 70mg with 7.0 mg carbidopa, or placebo), time point (15, 30, 45, 60, 90 or 120 minutes for INP103 and benserazide [C1, C2, C3] and 30, 60, 90, 120 minutes for INP103 and carbidopa [C4])) and the interaction between treatment group and time point as fixed factors. The baseline score will be included as a covariate. The focus will be on the estimation of changes within each treatment group. An unstructured covariance structure will be used for the MMRM. In case the model does not converge with the unstructured covariance structure, the heterogeneous compound symmetry (CSH) or heterogeneous Toeplitz structure (TOEPH) will be used instead. The denominator degrees of freedom will be computed using the Kenward-Roger method. The least square (LS) means, standard errors and two-sided 95% confidence intervals will be provided for changes within each treatment group. In addition, the differences between each treatment group and placebo will be estimated.

The cumulative proportion of responders will be summarized descriptively by treatment group and time point.

The endpoint related to time of response and time to ON will be evaluated with Kaplan-Meier methods. The figures of Kaplan-Meier estimate and summary statistics (25th percentile, median, and 75th percentile and their 95% confidence intervals) will be presented.

For subjects who received study drug administration and achieve response within 120 minutes post dosing, the duration of response will be summarized by treatment group. If the subject did not achieve response after 120 minutes post dosing, this subject will be regarded as censored and the duration of response will be treated as missing.

The AUC of MDS-UPDRS Part III scores from pre-dose to 15, 30, 45, 60, 90 and 120 minutes will be calculated as AUC_{0-15} , AUC_{0-30} , AUC_{0-45} , AUC_{0-60} , AUC_{0-90} and AUC_{0-120} (omitting AUC_{0-15} and AUC_{0-45} for Cohort 4). These AUC parameters will be summarized by treatment groups as well as analysed with an Analysis of Covariance (ANCOVA) model with treatment group as a fixed factor and baseline MDS-UPDRS Part III score as a covariate. The least square (LS) means, standard errors and two-

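### SAP 10.5's crediting rule overcounts duration of response at onset and undercounts it at offset, by amounts that depend on the cohort's rating times

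*SAP*

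**What the plan says.** SAP 10.5 defines duration of response as the "sum of all time intervals which observed a response" and explains this by a worked table. Each Yes rating is credited with the time back to the previous rating. For the 45-minute row that is "Actual time at '45 mins post-dose' minus the Actual time at '30 mins post-dose", and the 30-minute rating in that row's interval is No. For the first rating it is "Actual time at '15 mins post-dose' minus the Actual time at 'Pre-dose", so the clock starts at the pre-dose rating and not at dosing. Each No rating is credited 0, including the two (30 and 60 minutes) that follow a Yes.

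SAP 10.4 dates onset differently: "The time to response is defined as time from first dosing to the FIRST response", that is, at the first responding rating itself.

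The rating times differ by cohort. Cohorts 1-3 are rated at 15, 30, 45, 60, 90 and 120 minutes; SAP 10.3 gives "30, 60, 90 or 120 minutes for C4". SAP 7.1 pools placebo subjects from all cohorts, so the pool holds 6 planned subjects on the fuller schedule and 2 to 3 on Cohort 4's.

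On subjects who never respond, SAP 10.5 says "The duration of response will be calculated for each subject", and its formula gives them 0. Protocol 12.5 says "this subject will be regarded as censored and the duration of response will be treated as missing". Protocol 12 adds: "The SAP will serve as a complement to the study protocol and supersedes it in case of differences".

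**The concern.** A rating shows status at one moment. When status changes between two ratings, the change happened somewhere in between. The SAP rule always places it at the start of the interval: an onset interval counts wholly as response, and an offset interval wholly as non-response. The first is an overcount and the second an undercount. They need not cancel, because the intervals differ in length (15 or 30 minutes) and because a response still present at the last rating has no offset interval.

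Two consequences follow. The minutes up to the first responding rating are counted twice, as waiting time in SAP 10.4 and as response in SAP 10.5. And since Cohort 4 has 30-minute steps from dosing, the same true response can give different durations in Cohort 4 and in Cohorts 1-3, with pooled placebo mixing the two.

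Duration is a listed secondary motor endpoint. SAP 3.3 sets no hypotheses and leaves comparison to description, so the tabulated minutes are what a reader will compare.

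**Working it through.** **Inputs.** Example clock times and statuses: SAP 10.5. Rating times: SAP 10.2 and 10.3. Onset convention: SAP 10.4. Onset times and true durations are not in the documents; those used in steps 3 to 5 are assumptions.

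**Formulas.** With rating times t(i), status r(i) = 1 for response and 0 otherwise, and r(0) = 0 at dosing:
- SAP rule: sum of [t(i) − t(i−1)] × r(i)
- Half-credit: sum of [t(i) − t(i−1)] × [r(i−1) + r(i)]/2

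**1. The SAP example.** Times 0, 15, 30, 45, 60, 91, 125 minutes; Yes at 15, 45, 91 and 125.
- SAP rule: 15 + 0 + 0 + 15 + 31 + 34 = 95, which reproduces the stated figure. (The 90- and 120-minute rows print the subtraction in reverse order; the positive 31 and 34 show what is meant.)
- Both ends Yes: 34.
- Opening without an observed response and ending Yes: 15 + 15 + 31 = 61, all credited.
- Opening Yes and ending No: 15 + 15 = 30, none credited.
- With at most one switch per interval, the ratings fit anything from 34 to 34 + 61 + 30 = 125 minutes.
- Half-credit: 34 + 61/2 + 30/2 = 79.5. The SAP value is 95 − 79.5 = 15.5 minutes higher.

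**2. Overlap with time to response.** A subject responding at every rating has a duration of 120 minutes on either schedule. Adding time to response gives 15 + 120 = 135 minutes (Cohorts 1-3) or 30 + 120 = 150 (Cohort 4) in a 120-minute window.

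**3. Sustained response, onset assumed uniform over 0-120 minutes (true mean 60).** An onset in an interval of length L has probability L/120 and a mean overcount of L/2, so the mean bias is the sum of L²/240.
- Cohorts 1-3: (4 × 15² + 2 × 30²)/240 = 2700/240 = +11.25 minutes.
- Cohort 4: (4 × 30²)/240 = 3600/240 = +15.0 minutes.
- Half-credit: 0 in both.

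**4. Single response, onset assumed uniform over 5-60 minutes, cut at 120.** Mean bias in minutes; the gap is the Cohort 4 mean minus the Cohorts 1-3 mean. Differences from the bias columns are rounding.

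| True response | SAP, C1-3 | SAP, C4 | SAP gap | Half, C1-3 | Half, C4 | Half gap |
|---|---|---|---|---|---|---|
| 30 | −4.1 | 0.0 | 4.1 | 0.0 | 0.0 | 0.0 |
| 45 | −4.1 | +1.4 | 5.5 | +2.0 | +1.4 | −0.7 |
| 60 | −8.2 | 0.0 | 8.2 | −0.7 | 0.0 | 0.7 |
| 75 | −4.8 | +3.4 | 8.2 | −1.4 | −0.7 | 0.7 |
| 90 | 0.0 | +8.2 | 8.2 | −0.7 | 0.0 | 0.7 |

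**5. Early onset, assumed within 5-15 minutes.** The first rating is then a response on both schedules.
- Sustained to 120 minutes: SAP rule 120 and 120. Half-credit 7.5 + 105 = 112.5 (Cohorts 1-3) and 15 + 90 = 105 (Cohort 4).
- True 60 minutes (offset at 65-75): SAP rule 60 and 60. Half-credit 7.5 + 45 + 15 = 67.5 and 15 + 30 + 15 = 60.
- In both cases the gap is 0 under the SAP rule and 7.5 minutes under half-credit.

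With onset within 15-30 minutes and a sustained response, the order reverses. The SAP rule gives 105 and 120 (gap 15); half-credit gives 97.5 and 105 (gap 7.5).

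**6. Common ratings.** On 30, 60, 91 and 125 minutes the SAP example gives 31 + 34 = 65 under the SAP rule and 15.5 + 34 = 49.5 under half-credit. The drop from 95 and 79.5 comes from the schedule, not from the crediting rule.

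**The case against.** Backward crediting is explicit and reproducible, and half-credit is only another convention. In step 4 half-credit is no better in 4 of 10 cells: Cohort 4 at 30, 45 and 60 minutes (identical) and Cohorts 1-3 at 90 minutes (0.0 against −0.7). Step 5 shows it creating a gap between schedules where the SAP rule leaves none. The different schedules are an openly stated design feature, and on a common schedule the SAP rule would also treat all groups alike. SAP 10 calls these analyses exploratory, SAP 10.5 plans only a summary by group, and the active groups have 6 to 9 subjects.

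Much of this stands. A reader might infer from the 0.7-minute figure that half-credit alone makes the cohorts comparable. It does not: that figure belongs to onset uniform over 5-60 minutes. Comparability has to come from common rating times.

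What remains is that the SAP rule always places a change of status at the start of the interval, which the ratings cannot show, and that this conflicts with the onset date in SAP 10.4. Nothing else in the documents corrects either.

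A reader might also infer that Protocol 12.5 settles the never-responder question. Under Protocol 12 the SAP prevails where the two differ, and it is unclear whether SAP 10.5 intends to differ. That calls for clarification only.

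**Conclusion.** The point holds as a flaw in the derivation. SAP 10.5 overcounts at onset, undercounts at offset, and counts the minutes before first response under two endpoints. The example and the totals of 135 and 150 minutes need no assumption about onset. The mean biases of +11.25 and +15.0 minutes rest on a sustained response with uniform onset over 0-120 minutes. The gaps of 4.1 to 8.2 minutes between schedules rest on uniform onset over 5-60 minutes.

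A reader might infer that the rule simply inflates duration. The documents do not support that: the net sign depends on the profile, and step 4 gives −8.2 minutes for a 60-minute response in Cohorts 1-3. Nor is any hypothesis test, power figure or planned placebo difference affected.

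The first interval also starts at the pre-dose rating. Protocol 7.4.1 leaves the order of pre-dose assessments to the site, so time before dosing can be credited as response. The example does not show this, and its size cannot be given from the documents.

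**What to change.** In SAP 10.5:

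- Start the first interval at actual dosing time with status non-responder, and use the recorded time from dosing for each rating (Protocol Table 1, footnote j).
- Give full credit when both ends of an interval are responses, half when status changes, and none when both are non-responses.
- For any reading across Cohort 4, Cohorts 1-3 and pooled placebo, derive duration from the common 30/60/90/120-minute ratings. Keep the full-schedule summary within Cohorts 1-3 and their own placebo subjects.
- As a clarification, state whether never-responders count as 0 or as missing, and show the number of responders.

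The cost is one derivation and some SAP wording, on data already collected. SAP 17.2.2 does not plan the duration table for the interim analysis, and SAP 2 allows amendment before final database lock. Cohort 1-3 subjects get two labelled durations, and cross-cohort readings lose the 15- and 45-minute ratings. Reported durations may rise or fall.

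Half-credit leaves residual bias: about 2.0 minutes at most in step 4, but 67.5 − 60 = 7.5 minutes in the early-onset 60-minute case for Cohorts 1-3. It also keeps half of the overlap with SAP 10.4 for a subject who responds at the first rating (7.5 or 15 minutes). Neither rule recovers a response that falls between ratings.
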